#### ***4.6.3 Randomisation of Patients to Treatment***

Randomisation of patients to treatment will occur during screening or on D1 after all screening procedures have been performed and eligibility for inclusion in the study has been confirmed. Each randomised patient will receive a unique randomisation number. Randomised patients who terminate their study participation for any reason, regardless of whether study drug was taken or not, will retain their randomisation number.

The Investigator will use IWRS for randomisation of patients. Details can be found in the study file.

## 5 STUDY DRUG

### 5.1 Identity

Rentschler Biotechnologie GmbH, Laupheim, Germany manufacture lyophilised FP-1201-lyo (recombinant human IFN beta-1a) and the matched placebo. Both FP-1201-lyo and placebo powders are free of animal serum and human serum albumin. Vetter Pharma International Services, Ravensburg, Germany manufacture pre-filled water for injection (WFI) diluent syringes.

A MixJect® transfer device will be used in this study. This MixJect® transfer device is a single unit for reconstituting a powdered drug with a diluent pre-filled syringe.

Upon reconstitution, the drug is available for immediate injection. The MixJect® transfer device enables the safe, rapid and easy preparation of lyophilised drugs. The MixJect® transfer device is manufactured by West Pharmaceutical Services GmbH, Germany/Medimop Medical Projects, Ra'anana, Israel. The device carries the CE mark and has 510(k) approval by the United States Food and Drug Administration.

Fisher Clinical Services Ltd, Horsham, UK, is responsible for the packaging of FP-1201-lyo and matched placebo in a carton box. The pre-filled WFI diluent syringe, the MixJect® transfer device and the reconstitution instructions are packaged in the accessorial carton kit. Fisher Clinical Services Ltd is responsible for distributing the investigational medicinal product to the study sites.

### 5.2 Administration

FP-1201-lyo 10 µg (or placebo) will be diluted in WFI near the patient/in the ICU. Once prepared, the dose must be administered to the patient immediately. The diluted FP-1201-lyo or placebo will be administered as an intravenous bolus injection via a central or peripheral line. The injection will be followed with a 5 mL flush of sterile saline (not provided).

FP-1201-lyo and placebo injections will be given once daily for 6 days. The injection should be given at the same time each day  $\pm 1$  hour providing the patient's condition allows this. If for any reason this is not possible, the treatment window may be extended by up to 4 hours. The reason for the delay must be entered in the e-CRF. Subsequent doses should not be delayed and should revert to the original time schedule (e.g., if the D1 dose was at 13:00, the D2 dose was delayed and given at 17:00, the D3 dose should be given at 13:00  $\pm 1$  hour).

No dose modifications or temporary cessations of study drug administration are allowed. If a delay beyond the 4-hour window described above is required, the patient must be withdrawn from study drug but all data must continue to be collected per protocol. Administration of a second course of study drug is not permitted.

### 5.3 Packaging, Labelling and Storage

FP-1201-lyo and matched placebo are packaged in a carton. The pre-filled WFI diluent syringe and the MixJect® transfer device are packaged in an accessorial carton kit.

Six investigational medicinal products and six accessorial carton kits are reserved for each patient to cover the 6-day treatment period.

Labelling will be prepared by Fisher Clinical Services Ltd to meet the local regulatory requirements.

All study drug supplies must be stored in accordance with the manufacturer's instructions, i.e., FP-1201-lyo and placebo are to be stored at 2–8°C and the accessorial carton kits are to be stored at room temperature. Until dispensed to the patients, the study drug will be stored in a securely locked area, accessible to authorised personnel only.

The investigational medicinal product and the accessorial carton kits are dispensed only by the Investigator or by a member of staff specifically authorised by the Investigator, or by a pharmacist, as appropriate.

#### **5.4 Blinding and Breaking the Blind**

The study will be performed in a double-blind manner. All study drugs will be supplied in identical vials and will be similar in colour and appearance, thereby enabling double-blind conditions.

The treating physician (investigator) is responsible for the medical care of the trial patient and the study set up allows the investigator to rapidly break the treatment code in an emergency situation.

The study blind should only be broken in a medical emergency (where knowledge of the study drug received would affect the treatment of the emergency) or as a regulatory requirement (e.g., for SAEs or death). Note that there is no specific antidote or method of removing the study drug from the body (such as dialysis) and the best available care for the patient should be continued.

If the blind is broken, the date, time and reason must be recorded in the patient's e-CRF and any associated AE report. It is the responsibility of the investigator to promptly document and explain any unblinding to the sponsor/CRO.

Detailed instructions for the use of the IWRS in order to break the study blind for a patient are provided in a separate document that will be filed in the Site File and Trial Master File. As well as the IWRS, a backup system enabling unblinding of treatment is provided to the sites.

After a patient has been unblinded data collection should continue as per protocol.

Suspected unexpected serious adverse reactions (SUSARs), which are subject to expedited reporting, should be unblinded before submission to the regulatory authorities and Independent Ethics Committees (IECs).

The overall randomisation code will be broken only for reporting purposes. This will occur once all D90 clinical data have been entered into the database and all data queries related to D90 have been resolved, and the assignment of patients to the analysis sets has been completed.

#### **5.5 Drug Accountability**

The Investigator is responsible for maintaining accurate study drug accountability records throughout the study.

Each dispensing of study drug will be documented in the e-CRF.

The Investigator is responsible for ensuring all unused medication is destroyed at the investigational site following the appropriate drug accountability procedures.

## **5.6 Compliance**

The study drug is administered intravenously at the study site, so it is not necessary to monitor patient compliance with the study drug regimen.

## **5.7 Previous and Concomitant Medications**

Any medication the patient takes other than the study drug between screening and D28, including herbal and other non-traditional remedies, is considered to be a concomitant medication. All concomitant medications must be recorded in the e-CRF except for nutritional and volume therapy, electrolyte support, vitamins and supportive therapies such as artificial tears, ointments, etc. The following information must be recorded in the e-CRF for each concomitant medication: generic name, route of administration, start date, stop date, dosage and indication. Any changes in the dosage or regimen of a concomitant medication must be recorded in the e-CRF. If a patient is discharged from the hospital prior to D28 then the patient must be instructed that the Investigator should be informed about additional medication up to D28.

Concomitant medications or therapies that are considered necessary for the patient's welfare and that will not interfere with the study drug may be given at the discretion of the Investigator.

All patients in this study will be managed with supportive care measures according to the best practice established locally in each ICU. Due consideration must be given to the study guidance on supportive measures given in Appendix 1, Section 11.1.

At screening, patients (or their relatives) will be asked what medications they have taken during the last month. In connection with the 6MWT at D180 and D360, patients (or their carers or relatives) will be asked what medications the patients have taken during the last 24 hours.

There are no prohibited co-medications in this study.

## 6 VARIABLES AND METHODS OF ASSESSMENT

The timing of the assessments of the variables is shown in the Schedule of Procedures (Table 5 in Section 7.1).

### 6.1 Efficacy Variables

The following efficacy variables will be assessed:

- Mortality
- Days on mechanical ventilation
- SOFA
- Days in ICU
- Days in hospital
- Days on vasoactive support
- Days on renal support
- Neutralising antibodies
- Biomarker MxA
- QoL
- Respiratory functioning (FEV1)
- Neurological functioning (6MWT)

#### 6.1.1 Primary Efficacy Variables

All-cause mortality will be assessed at D28 (primary) and also at D90 and D180, and at the extended long-term follow-up at D360. All deaths shall be recorded as SAEs up to D360. The patient's location at the time of death (ICU or hospital) will also be recorded.

For the composite primary endpoint, ventilator-free days (VFDs) will be calculated. A patient will be reported as ventilator free after **two consecutive calendar days** of unassisted breathing (UAB). UAB is defined as:

- Spontaneously breathing with face mask, nasal prong oxygen or room air
- T-piece breathing
- Tracheostomy mask breathing
- CPAP  $\leq 5$  cmH2O without pressure support or intermittent mandatory ventilation assistance
- Use of CPAP or BIPAP solely for sleep apnoea management

Patients still on positive pressure ventilation/receiving assisted breathing who are transferred to another hospital or healthcare facility prior to D28 will be followed up to assess the VFD outcome at D28.

These variables will also be assessed at D90 in an exploratory analysis.

#### 6.1.2 Secondary Efficacy Variables

##### 6.1.2.1 Sequential Organ Failure Assessment

Organ failure status will be assessed using the SOFA score, which assesses six organ systems: respiration, coagulation, liver, cardiovascular, central nervous system and

renal (Table 2). (Ref: Grissom et al 2010) A patient will be defined as being free of organ failure when the SOFA score is zero. The score will be assessed pre-dose on D1 and daily up to D14, at D21 and at D28 while the patient is in the ICU, based on worst daily values.

The SOFA score variables to be assessed daily from baseline to D28/leaving the ICU are:

- PaO2/FiO2 (mmHg)
- Platelets × 10^3/mm^3
- Bilirubin (µmol/L or mg/dL)
- Hypotension/use of vasopressors
- Glasgow Coma Scale (GCS)
- Creatinine (µmol/L or mg/dL)

**Table 2 SOFA Scoring**

SOFA score	0	1	2	3	4
Respiration					
PaO 2 /FiO 2 , mmHg	>400	>300–≤400	>200–≤300	>100–≤200	≤100
				---with respiratory support---	
Coagulation					
Platelets × 10  /µL	>150	>100–≤150	>50–≤100	>20–≤50	≤20
Liver					
Bilirubin, mg/dL (µmol/L)	<1.2 (<20)	≥1.2–<2.0 (≥20–<33)	≥2.0–<6.0 (≥33–<102)	≥6.0–<12.0 (≥102–<204)	≥12.0 (≥204)
Cardiovascular					
Hypotension a	No hypo- tension	MAP <70 mmHg	Dopamine ≤5 or dobutamine (any dose)	Dopamine >5 or epinephrine ≤0.1 or norepinephrine ≤0.1	Dopamine >15 or epinephrine >0.1 or norepinephrine >0.1
Central nervous system					
Glasgow Coma Scale b, c	15	13–14	10–12	6–9	<6
Renal					
Creatinine, mg/dl or µmol/L or urine output	<1.2 <110	≥1.2–<2.0 ≥110–<171	≥2.0–<3.5 ≥171–<300	≥3.5–<5.0 ≥300–<440 or <500 mL/d	≥5.0 ≥440 or <200 mL/d

a Adrenergic agents administered for at least 1 hour (doses are given in µg/kg/min).

b For patients who are intubated, the verbal response is scored as:

5 – Seems able to talk

3 – Questionable ability to talk

1 – Generally unresponsive.

c For patients who are sedated use an estimated score for GCS (the assumption is 15, if no other factors than sedation affect GCS)

Abbreviations: MAP=mean arterial pressure; PaO2/FiO2=partial pressure of oxygen/fraction of inspired oxygen; SOFA=Sequential Organ Failure Assessment.

#### 6.1.2.2 Renal Support

Any renal support given to the patient will be recorded on a specific page in the e-CRF.

#### 6.1.2.3 Vasoactive Support

Any vasoactive support given to the patient will be recorded on a specific page in the e-CRF. Vasoactive support includes: catecholamine and non-catecholamine vasopressors, inotropes and vasodilating agents.

#### 6.1.2.4 Neutralising Antibodies to Interferon Beta-1a

Blood samples (2.5 mL) will be taken on D1 pre-dose (baseline) and D28 (or on last day in ICU or at withdrawal, if earlier) to determine the presence of neutralising antibodies to IFN beta-1a.

Neutralising antibody blood sample preparation and sample storage details are provided Laboratory Manual. It is essential that the actual time and date of collection of each antibody sample be recorded in the sample collection form provided with the laboratory kits.

Neutralising antibody samples will be analysed centrally at Wieslab AB, Malmö, Sweden.

#### 6.1.2.5 Myxovirus Resistance Protein A

Whole blood samples (2 mL) will be taken pre-dose on D1 and daily from D2 to D14 for analysis of MxA levels. For details of sample preparation and storage refer to the Laboratory Manual. MxA samples will be analysed centrally at Wieslab AB.

#### 6.1.2.6 Quality of Life, Respiratory Functioning and Neurological Functioning

Health-related QoL (EQ-5D-3L), respiratory functioning via FEV1 and neurological functioning via the 6MWT, will be assessed at D180 (6 months). If the patient is unable to come to the hospital for the FEV1 and 6MWT assessments, the QoL information should still be obtained by telephone interview. Additional data will be collected at D360 (12 months) to form part of the extended long-term follow-up.

##### EQ-5D-3L Questionnaire

EQ-5D-3L provides a simple descriptive profile and a single index value of health status that can be used in clinical research and economic evaluation of healthcare as well as in population health surveys. The questionnaire is cognitively undemanding, designed for self-completion and takes only a few minutes to complete.

At the time when the patients are screened/enrolled in the study it may not be possible to directly obtain baseline information on their pre-admission QoL. In these cases, a description of the patient's pre-study functioning at home should be obtained from their relatives, recorded in the e-CRF and used as the reference value. This information will be checked by the patient at a later stage and correspondingly updated in the e-CRF.

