b These assessments will be done on the day the patient leaves the ICU, which will either be on D28 or earlier, according to the clinical progress of the patient. If the patient is still in the ICU on D28, the next visit or telephone contact will be at D90. If a patient leaves the ICU before D28, the survival status and other endpoints must be assessed on D28.

c D28 procedures apply for patients leaving the ICU before D28 and for patients withdrawing from the study before D28. For patients withdrawing from the study before D28 a sample should be taken for neutralising antibodies on the day they leave the ICU.

d D90 can either be a visit or telephone contact.

e Reconfirm inclusion/exclusion criteria before dosing, including that patient requires mechanical ventilation and is in the ICU (patients requiring ECMO after randomisation but before the first dose of IMP may still be included).

f Randomise after consent obtained and once eligibility criteria confirmed.

g Within 24 hours of ICU admission

h Within 1 hour pre-dose.

i Baseline EQ-5D-3L to be obtained from relatives and checked later with patient.

j For APACHE II scoring.

k Samples should be taken in the morning between 04:00 and 10:00.

l Medicines and therapies in previous month.

m Adverse events will be recorded after informed consent is obtained.

n Deaths are reported as SAE

o if it is possible to be performed by the investigator

Abbreviations: APACHE II=Acute Physiology and Chronic Health Evaluation; CD=cluster of differentiation; CT=computerised tomography; D=study day; ECG=electrocardiogram; ECMO=extra-corporeal membrane oxygenation; EQ-5D-3L=EuroQol 5-Dimensions 3-Levels questionnaire; FEV1=forced expiratory volume in 1 second; GCS=Glasgow Coma Scale; ICU=intensive care unit; IFN=interferon; MxA=myxovirus resistance protein A; PaO2/FiO2=partial pressure of oxygen/fraction of inspired oxygen; PIM=potential inflammatory marker; SOFA=Sequential Organ Failure Assessment; 6MWT=6-minute walk test.

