### **5.4.2 Quality Of Life Evaluations**

General assessment of health is performed through a quality of life questionnaire (QOL). The EuroQol 5-Dimensions 3-Levels questionnaire (EQ-5D-3L) is administered at Day 1 Pre-dose, Day 180 and Day 360.

An EQ VAS score (ranging from 0-100) is measured (0= Worst imaginable health state, 100= Best imaginable health state) together with sub scores for Mobility, Self-care, Usual Activities, Pain/Discomfort and Anxiety/Depression. Each sub score ranges from 1 to 3 with 1 representing the best case and 3 the worst case.

The change from baseline (Day 1 Pre-dose) will be derived.

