#### ***6.2.4.5 Sequential Organ Failure Assessment (SOFA) Analysis***

Total scores and Change from baseline scores (Day 1 Pre-dose) assessed daily up to Day 14 and then at Day 21 and Day 28 (In or Out of the ICU) or Early Termination, together with the derived Last observation performed will be numerically summarised according to Treatment group (FP-1201-lyo/Placebo), Severity of ARDS (Moderate/Severe) and Overall using the FAS population. Separate supporting summaries by Country will be included.

The contributing Cardiovascular, Respiratory, Coagulation, Hepatic, Renal and CNS organ sub scores will be similarly presented.

The Total SOFA score at the Last observation performed will be analysed using an Analysis Of Covariance (ANCOVA) model (Ref 8) this will use change from baseline as the response variable and will include Treatment group (FP-1201-lyo/Placebo), Severity of ARDS (Moderate/Severe) and Country (1-8) as fixed effect factors. The Baseline value will also be used as a covariate term in the model.

Model assumptions of normality and constant variance will be investigated and if necessary an alternative model or data transformation will be substituted.

Model estimates (LS means and a 95% confidence interval for the treatment difference) will be presented. Homogeneity of treatment effect will be assessed by obtaining the difference in LS means together with 95% confidence intervals for the categories of ARDS severity using the ANCOVA model with the addition of a treatment by ARDS severity interaction term and displaying these in a Forest Plot.

Sub scores will not be analysed.

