##### ***6.2.5.2 Quality Of Life Questionnaire Analyses***

The EQ-5D-3L is performed at Day 1 Pre-dose, Day 180 and Day 360. The EQ VAS score and sub scores will be numerically summarised for actual values and change from baseline by Treatment group (FP-1201-lyo/Placebo), Severity of ARDS (Moderate/Severe) and Overall for each assessment time using the FAS population only, although this sample will exclude any patients who did not survive to Day 180 or Day 360. Separate supporting summaries by Country will not be included.

The EQ VAS score will be analysed using an Analysis Of Covariance (ANCOVA) model as described for Total SOFA scores in Section 6.2.5.5. A separate analysis will be performed at each assessment time (Day 180 and Day 360) although p-values for inferential purposes will not be presented.

Sub scores will not be analysed.

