### ***6.2.5.3 Respiratory And Neurological Function Assessment***

#### ***6.2.5.3.1 Respiratory Function (FEV-1) Analyses***

FEV-1 measured at Day 180 and Day 360 will be numerically summarised using actual values by Treatment group (FP-1201-lyo/Placebo), Severity of ARDS (Moderate/Severe) and Overall for each assessment time using the FAS population only. Again this group will only include survivors at the time of assessment. Separate supporting summaries by Country will not be included.

The FEV-1 will be analysed using an ANCOVA model (as for the Total SOFA scores in Section 6.2.5.5 but excluding the baseline covariate).

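### The relatives' pre-dose EQ-5D-3L may be updated after a later check by the patient, so a post-dose value can enter the baseline of the quality-of-life ANCOVA

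*Protocol*

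**What the plan says.** **Collection.** Protocol 6.1.2.6 (EQ-5D-3L Questionnaire) covers patients who cannot report at enrolment: "a description of the patient's pre-study functioning at home should be obtained from their relatives, recorded in the e-CRF and used as the reference value". It continues: "This information will be checked by the patient at a later stage and correspondingly updated in the e-CRF". Footnote i of the schedule repeats this: "Baseline EQ-5D-3L to be obtained from relatives and checked later with patient". The same footnote stands under SAP Table 2. Neither document sets a time for the check.

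**Definition of baseline.** Protocol 8.2.1.1 takes the latest valid assessment before dosing. SAP 5.9.1 takes Day 1 Pre-dose. For EQ-5D-3L, SAP 5.4.2 says: "The change from baseline (Day 1 Pre-dose) will be derived".

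**Analysis.** SAP 6.2.5.2: "The EQ VAS score will be analysed using an Analysis Of Covariance (ANCOVA) model as described for Total SOFA scores in Section 6.2.5.5". The cross-reference is wrong, because 6.2.5.5 concerns ventilation-free survival at Day 90. The SOFA model is in 6.2.4.5, has change from baseline as the response, and adds: "The Baseline value will also be used as a covariate term in the model". For FEV-1 the SAP makes an explicit exception ("but excluding the baseline covariate"), and it does likewise for the 6MWT. EQ VAS has no such exception, so its baseline stays in the model.

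**Status.** Protocol 8.5.2.5 limits these analyses to survivors, with summary statistics and descriptive confidence intervals. SAP 6.2.5.2 presents no p-values for inference.

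**The concern.** Every patient is intubated and ventilated at entry (Protocol 4.1), and Protocol 9.6 expects most to be too sedated to consent. Ratings by relatives are therefore likely to be common, and the patient's check will normally come after dosing. A site that follows 6.1.2.6 ends up with one e-CRF field. For some patients it holds a rating made before treatment, and for others a recollection recorded after it.

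An ANCOVA covariate should be unaffected by treatment. Blinding does not secure that here: treatment may change current health, and current health may colour the memory of earlier health. Who is able to check the value also depends on survival and recovery, so the mix of relatives' and patients' ratings can differ between arms. At stake is the EQ VAS treatment difference with its 95% CI at D180 and D360, and the change-from-baseline summaries of the EQ VAS and the five sub scores.

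**Working it through.** The documents give no effect size, SD or power for EQ-5D-3L, so there is no stated figure to reproduce. All inputs below are assumptions except the planned numbers and mortality rates.

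**1. General result.** Let delta be the difference between arms in the stored baseline that treatment has caused, and beta the within-arm slope of the follow-up score on that baseline.
- ANCOVA shift = -beta x delta, the same whether the response is the score or its change.
- Shift in the raw change-score difference = -delta.
- For delta = 2 points and beta = 0.2 to 0.6, the ANCOVA shift is -0.4 to -1.2. For delta = 5 it is -1.0 to -3.0. If recall and updating do not depend on treatment, delta = 0 and there is no shift.

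**2. Recall pulled towards the D180 score itself (upper scenario).** Stored baseline B* = (1-k)B + kY, with equal SDs (20) and correlation r = 0.4 between true baseline B and D180 score Y. Then delta = k x effect, and

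beta = [(1-k)r + k] / [(1-k)^2 + k^2 + 2k(1-k)r]; proportional loss = k x beta.

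| k | beta | loss | estimate if true effect is 8 |
|---|---|---|---|
| 0.1 | 0.46/0.892 = 0.516 | 5% | 7.59 |
| 0.2 | 0.52/0.808 = 0.644 | 13% | 6.97 |
| 0.3 | 0.58/0.748 = 0.775 | 23% | 6.14 |

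The raw change-score difference loses the full fraction k: 7.2, 6.4 and 5.6.

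**3. Check made earlier (lower scenario).** Recall is pulled towards health at the check, H. Assume correlation 0.5 between H and Y, 0.4 between H and B, and half the effect present at the check. The 2k(1-k)r term now uses the H-B correlation, so the denominators are unchanged. The numerator becomes (1-k)(0.4) + 0.5k, and the loss is 0.5 x k x beta.
- k = 0.1: 0.5 x 0.1 x 0.41/0.892 = 2.3%
- k = 0.2: 0.5 x 0.2 x 0.42/0.808 = 5.2%
- k = 0.3: 0.5 x 0.3 x 0.43/0.748 = 8.6%

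**4. Opposite direction.** If the patient contrasts past with present health, k is negative. With k = -0.1 in step 2, beta = 0.34/1.132 = 0.300 and the estimate grows by 0.1 x 0.300 = 3%.

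**5. Simulation under another recall model.** Recall = true baseline + kappa x current health + noise (SD 10); relatives' rating = true baseline + noise (SD 10). True effect 5, SD 20, correlation 0.4, 4000 runs, 115 survivors per arm. The plan's D28 mortality gives at most 150 x 0.85 + 150 x 0.70 = 232.5 survivors.

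| kappa | ANCOVA, relatives' value | ANCOVA, all updated | ANCOVA, half updated | Change score, all updated |
|---|---|---|---|---|
| 0 | 4.98 | 4.98 | 4.98 | 4.96 |
| 0.1 | 4.99 | 4.80 | 4.86 | 4.49 |
| 0.2 | 4.98 | 4.56 | 4.86 | 4.01 |
| 0.4 | 5.00 | 4.06 | 4.56 | 2.96 |

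The second column is from the all-updated runs. The pre-dose rating recovers the simulated effect whatever the recall bias.

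**6. Scale.** With 115 per arm, the residual SD is 20 x sqrt(1 - 0.4^2) = 18.3, and the 95% half-width is 1.96 x 18.3 x sqrt(2/115) = 4.7 points. The k = 0.2 bias in step 2 is 8 - 6.97 = 1.0 point.

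**The case against.** The best defence is that both documents already define baseline as pre-dose. On that definition a later edit is not baseline, whatever the e-CRF holds. Nor does 6.1.2.6 order wholesale replacement: the value changes only where the patient disagrees. The derivation rules (SAP Appendix 4) and the D180/D360 table shells are not in the text available, and Protocol 8.8.4 assigns the follow-up analyses to a separate SAP, so a rule may exist elsewhere. This stands in part. A reader might infer that the SAP plans to adjust for a post-treatment value. It does not say so. What the documents show is a conflict between the data-entry instruction and the baseline definition, with no rule in the available text to settle it.

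Three other readings go too far.
- **The relatives' rating is lost.** Protocol 9.1.1 logs corrections in an audit trail. No available text calls for using the logged original.
- **The bias runs towards no effect.** No passage supports a direction, and step 4 shows the reverse.
- **Fixing the baseline makes the comparison unbiased.** It removes this one source. The analysis is still confined to survivors, under planned mortality of 30% versus 15%.

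It is also fair that relatives' ratings are noisier, that subtracting them from a patient's own score mixes respondents, and that some patients may have no such rating. Where no personal representative is available, for instance, a doctor unconnected with the study may consent (Protocol 9.6.4).

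**Conclusion.** The point holds as a minor one. Followed as written, the e-CRF instruction can put a post-dose recollection into a field that the SAP treats as pre-dose, and from there into the EQ VAS covariate and the change scores.

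The ANCOVA estimate shrinks by about 2-5% at k = 0.1 and about 9-23% at k = 0.3. Where it falls in each range depends on how closely health at the check tracks health at D180. These figures assume that every analysed value is updated and that recall is pulled towards current health; partial updating lowers them. In steps 2 and 3 the percentages depend on the correlations, not on the SD or effect size, provided the SDs are equal. There is no bias if neither recall nor updating depends on treatment.

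The consequence is confined to a descriptive long-term endpoint in survivors, outside both multiplicity hierarchies (Protocol 8.5.2.1.1, SAP 6.1.3). The primary endpoint, mortality and error control are untouched.

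**What to change.** 1. **e-CRF and Protocol 6.1.2.6:** store the pre-dose rating and the later patient-checked rating in separate dated fields, each with respondent type. Recover originals already changed from the audit trail.
2. **SAP 5.4.2 and 6.2.5.2:** state that the value recorded before the first dose, by patient or relative, is the ANCOVA baseline and the reference for change. Use the patient-checked value only in a sensitivity analysis.
3. **No pre-dose value:** keep the patient in the model with a missing-baseline indicator, or with a single imputed baseline that uses no post-dose data. This needs a stated exception to SAP 5.9.6, which plans no imputation. Fitting the follow-up score as the response leaves the treatment estimate unchanged and avoids an undefined change score.
4. **Cross-reference:** in SAP 6.2.5.2 replace 6.2.5.5 with 6.2.4.5. The same wrong number appears in 6.2.5.3.1 and 6.2.5.3.2.

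The cost is one additional rating field with its date and respondent type, a few sentences, and an audit-trail extraction, none of which needs unblinding. The downside is a noisier covariate, and raw change scores that compare a relative's rating with the patient's own.
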